8.1.10 Time to the 1st Recurrent Transfusion Event from the 1st Transfusion Event

Transfusion data will be summarized by RBC transfusion and platelet transfusion separately.

Time to 1st Recurrent RBC/Platelet Transfusion from the 1st Transfusion After Achieving CR

Time to 1st recurrent RBC/platelet transfusion from the 1st transfusion after achieving CR will be defined as number of days from the 1st transfusion after achieving CR to the first recurrent RBC/platelet transfusion. If a subject only has one RBC/platelet transfusion after achieving CR, the subject's data will be censored at 30 days after the last dose date of study drug or death of any cause, whichever occurs earlier. Only subjects with best response CR with at least one subsequent transfusion will be included in the analysis.

Time to 1st Recurrent RBC/Platelet Transfusion from the 1st Transfusion After Achieving CRh

Time to 1st recurrent RBC/platelet transfusion from the 1st transfusion after achieving CRh will be defined as number of days from the 1st transfusion after achieving CRh to the first recurrent RBC/platelet transfusion. If a subject only has one RBC/platelet transfusion after achieving CRh, the subject's data will be censored at 30 days after the last dose date of study drug or death of any cause, whichever occurs earlier. Only subjects with best response CRh with at least one subsequent transfusion will be included in the analysis.

Time to 1st Recurrent RBC/Platelet Transfusion from the 1st Transfusion After Achieving CR/CRh

Time to 1st recurrent RBC/platelet transfusion from the 1st transfusion after achieving CR/CRh will be defined as number of days from the 1st transfusion after achieving CR/CRh to the first recurrent RBC/platelet transfusion. If a subject only has one RBC/platelet transfusion after achieving CR/CRh, the subject's data will be censored at 30 days after the last dose date of study drug or death of any cause, whichever occurs earlier. Only subjects with best response CR/CRh with at least one subsequent transfusion will be included in the analysis.

Time to 1st Recurrent RBC/Platelet Transfusion from the 1st Transfusion for non-CR/CRh Subjects

Time to 1st recurrent RBC/platelet transfusion from the 1st transfusion will be defined as number of days from the 1st RBC/platelet transfusion to the first recurrent RBC/platelet transfusion. If a subject only has one RBC/platelet transfusion, the subject's data will be censored at last dose of study drug + 30 days or death of any cause, whichever occurs earlier. Only subjects with best response of non-CR/CRh and with at least one subsequent transfusion will be included in the analysis.

8.1.11 Additional Sensitivity Analyses of Efficacy Variables

Duration of Response

Sensitivity analyses for duration of CR + CRh, duration of CRh, and duration of CR will be provided based on different censoring methods.

1. For subjects who had post treatment therapy before disease progression events or death due to disease progression, two methods will be performed:
 - Method 1: this subject data will be censored at the date of last disease assessment before starting post treatment therapy;

- Method 2: this subject's data will be considered as an event at the date of last disease assessment before starting post treatment therapy.
2. For subjects who are lost to follow-up without disease progression or death due to disease progression documented, last disease assessment (bone marrow and hematology lab collations) will be considered as an event.
 3. If a disease progression or death due to disease progression event occurred more than 91 days (3 cycles) from the last disease assessment (bone marrow collection or hematology lab collection), this subject will be censored at the date of last disease assessment prior to the disease progression or death due to disease progression event.

Details of the censoring method for sensitivity analyses of duration of response are provided below in [Table 5](#).

Table 5. Censoring Methods for Analyses of CR + CRh, CR, and CRh

Situation	Date of Progression/Date of Censor	Outcome
Post-treatment therapy initiated with no disease progression documented	Date of last disease assessment before initiating post-treatment therapy (bone marrow or hematology lab)	Method 1) Censored
Post-treatment therapy initiated with no disease progression documented	Date of last disease assessment before initiating post-treatment therapy (bone marrow or hematology lab)	Method 2) Event
Loss to follow-up without disease progression or death due to disease progression documented	Date of last disease assessment (bone marrow or hematology lab)	Event
Death or disease progression occurred after missing a scheduled disease assessments (disease progression or Death due to disease progression occurred > 91 days of last disease assessment)	Date of last disease assessment (bone marrow or hematology lab)	Censored

Overall Survival

Sensitivity analyses for OS will be provided based on different censoring methods as shown in [Table 6](#). OS analysis including all deaths collected in the extracted database will also be performed.

Table 6. Censoring Methods for Analyses of OS

Situation	Date of Progression/Date of Censor	Outcome
Withdrawal consent for survival follow-up	Last known alive date	Event
Post-treatment therapy	Start date of post-treatment therapy	Censored

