5.3.1 Safety and Efficacy Measurements Assessed and Flow Chart

This study is designed to assess pharmacokinetic, pharmacodynamic, pharmacogenetic, efficacy, and safety data. Study procedures described in this protocol are summarized in Table 3.

Table 3. Study Activities (Phases 1 and 2 {Including Cohort C})

Procedures	Scr ^a	Day -1	Cycle 1					Day 1 of Cycle 2 and Day 1 of Every Cycle Thereafter (± 3 Days)	Cycle 2 Day 1, Cycle 4 Day 1, and Every 3 Cycles Thereafter (± 7 Days)	Final Visit ⁿ	30-Day Safety F/U	PT F/U ^u (± 1 Week)
			Day 1	Day 2	Day 3	Day 4	Day 5					
Informed Consent	X ^b											
Medical/Oncology History Assessment	X		X ^c									
Cytogenetic Assessment ^d	X											
AE/Concomitant Medication Assessment ^v	X	X	X	X	X	X	X	X		X	X	
Tumor Lysis Syndrome Prophylaxis ^e		X	X	X	X	X	X					
Physical Exam (including weight) ^{f,v}	X ^h		X				X ⁱ	X ^j		X ^j	X ^j	
Vital Signs ^{f,v}	X	X	X	X	X	X	X	X		X	X	
ECOG Performance Status ^{f,v}	X		X					X		X	X	
Hematology ^{f,g,v}	X		X	X	X	X	X	X		X	X	X
Chemistry ^{e,f,v}	X ^k		X	X	X	X	X	X ^k		X ^k	X	
Coagulation ^{f,v}	X		X					X ^l		X	X	
Urinalysis ^{f,v}	X											
12-lead ECG ^{m,v}	X									X ^o		
MUGA (preferred)/2D Echocardiogram w/Doppler ^{m,p}	X											
Clinical Disease Progression Assessment									X	X		X
Bone Marrow Aspirate and Biopsy for Response Assessment	X ^q								X ^r	X		

Table 3. Study Activities (Phases 1 and 2 {Including Cohort C}) (Continued)

Procedures	Scr ^a	Day -1	Cycle 1					Day 1 of Cycle 2 and Day 1 of Every Cycle Thereafter (± 3 Days)	Cycle 2 Day 1, Cycle 4 Day 1, and Every 3 Cycles Thereafter (± 7 Days)	Final Visit ⁿ	30-Day Safety F/U	PT F/U ^u (± 1 Week)
			Day 1	Day 2	Day 3	Day 4	Day 5					
Dispense Subject Calendar/Diary							X ^s	X				
Collect Study Drug and Subject Calendar/Diary ^w								X		X		
Survival Assessments ^t											X	

Scr = Screening; F/U = Follow-Up; PT = Post-Treatment

- a. Screening procedures must be performed within 21 days prior to initial study drug administration.
- b. Obtain informed consent prior to performing any screening or study-specific procedures.
- c. On Cycle 1 Day 1, any additional medical history that is observed after signing of the informed consent but prior to initial study drug administration and not considered related to study-required procedures will be recorded in the subject's medical history.
- d. Cytogenetic testing should be performed if not completed within 3 months prior to Screening.

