- u. Post Treatment visits will be performed every 12 weeks (\pm 1 week) for up to 1 year after last subject's last dose or possibly sooner if all patients have discontinued and most patients have expired. Survival assessments will be performed every 12 weeks, beginning when subjects develop progressive disease, for 1 year after the last subject's last dose or possibly sooner if all patients have discontinued and most patients have expired.
- v. Procedure may be performed in the subject's home or local hospital/clinic by adequately trained personnel if required due to COVID-19 restrictions.
- w. Venetoclax may be shipped directly to a subject's home only if required due to COVID-19 restrictions.

Note: Refer to [Table 4](#) for treatment schedule.

Table 4. Treatment Schedule (Phase 1 and Initial Phase 2)

	Cycle 1 ^a			Cycle 2 ^a and Subsequent Cycles ^a		Continuation of Venetoclax Monotherapy Only ^{a,b}
	Day 1	Day 2 – 10	Days 11 – 28	Days 1 – 10	Days 11 – 28	Days 1 – 28
Venetoclax		X	X	X	X	X
Cytarabine	X	X		X		

a. Cycle length = 28 Days.

b. Subjects enrolled in either Phase 1 or Phase 2 portions may discontinue LDC but continue receiving venetoclax once daily as monotherapy for up to 4 years following the first dose of the last subject enrolled on study provided they continue to tolerate venetoclax, have no evidence of disease progression, and do not meet any criteria for subject discontinuation (Section 5.4.1).

Table 5. Treatment Schedule (Phase 2 Cohort C)

	All Cycles ^a	
	Day 1 – 10	Days 11 – 28
Venetoclax ^b	X	X
Cytarabine ^b	X	

- a. Cycle length = 28 Days.
- b. Subjects enrolled in the Cohort C portion may discontinue LDC but continue receiving venetoclax once daily as monotherapy for up to 4 years following the first dose of the last subject enrolled on study provided they continue to tolerate venetoclax, have no evidence of disease progression, and do not meet any criteria for subject discontinuation (Section 5.4.1). Additionally, should a subject discontinue venetoclax or LDC due to reasons other than progression or unacceptable toxicity, subjects may be allowed to subsequently resume treatment with venetoclax and/or LDC upon discussion between the AbbVie medical monitor and the investigator.

Table 6. Schedule of Biomarker/Pharmacogenetic/Pharmacodynamic Sample Collection (Phase 1 and 2 {Including Cohort C})

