An Interactive Response Technology (IRT) system will be utilized to register subjects. Once the subject has signed the informed consent the site will obtain a screening (subject) number via the IRT system. Once the screening number is assigned, if the subject is not enrolled into the study, the reason for screen failure will be documented in the source document and will be captured in the eCRF.

The results of all screening evaluations must be within clinically acceptable limits, upon review by the investigator before a subject can be administered study drug. Subjects will not be enrolled in the study if laboratory or other screening results are unacceptable.

Subjects who complete all screening procedures and meet the eligibility criteria in Section 5.2.1 and none of the exclusion criteria in Section 5.2.2 will proceed to enrollment.

Post-Treatment Follow-Up Visit(s)

For subjects who discontinue study treatment for reasons other than disease progression, the following post-treatment assessments will be performed every 12 weeks (\pm 1 week) until criteria are met for discontinuation from the study (e.g., disease progression, death or a subject's refusal of the Post-Treatment visits) for a period of 1 year after last subject's last dose or possibly sooner if all patients have discontinued and most patients have expired:

- Hematology
- Disease Assessment

Survival Assessment(s)

Survival information (e.g., date and cause of death, post-treatment cancer therapies, including transplantation) will be collected once the subject's disease has progressed via telephone calls (e.g., to subject or family member) and/or clinical visits at 12 weeks intervals (\pm 1 week) after the subject's last study visit for a period of 1 year after last subject's last dose or possibly sooner if all patients have discontinued and most patients have expired.

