Post-treatment assessment will be performed every 12 weeks (± 1 week) until discontinuation from the study (e.g., disease progression death or a subject's refusal of the Post-Treatment visits) for a period of 1 year after last subject's last dose or possibly sooner if all patients have discontinued and most patients have expired.

Survival information (e.g., date and cause of death, post-treatment cancer therapies, including transplantation) will be collected once the subject's disease has progressed via telephone calls (e.g., to subject or family member) and/or clinical visits at 12 weeks intervals (± 1 week) after the subject's last study visit for a period of 1 year after last subject's last dose or possibly sooner if all patients have discontinued and most patients have expired.

Additionally, in the event a subject withdraws from the study, PD and predictive samples stored for long term (up to 20 years) biomarker research will also be destroyed. In the event that destruction is not possible, they will no longer be linked to the subject. If the subject changes his/her mind, and the samples have already been tested, those results will still remain as part of the overall research data. In the event of a subject's death or loss of

competence, the samples and data will continue to be part of AbbVie's research, but will not be stored more than 20 years.

COVID-19 Pandemic-Related Acceptable Protocol Modification

During the COVID 19 pandemic, it has been necessary to employ mitigation strategies to enable the investigator to ensure subject safety and continuity of care. Refer to the Section 5.3.1.1, Study Procedures and Table 3 for details on how to handle study activities/procedures accordingly. Study drug interruptions due to COVID-19 restrictions should be captured in EDC.

The investigator should contact the sponsor medical contact before discontinuing a subject from the study for a reason other than "planned per protocol," to ensure all acceptable mitigation steps have been explored.

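### The 91-day missed-assessment rule in the duration-of-response sensitivity analysis is not three cycles, and may censor relapses found at on-time post-treatment visits

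*SAP*

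**What the plan says.** Item 3 under Duration of Response in SAP 8.1.11 applies to a progression, or a death due to progression, that "occurred more than 91 days (3 cycles) from the last disease assessment". An assessment is either kind of sample: "bone marrow collection or hematology lab collection". Such a subject is censored at the last assessment before the event. Table 5 gives the situation the rule is meant to catch: "Death or disease progression occurred after missing a scheduled disease assessments".

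The relevant intervals are in the protocol:

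- Tables 4 and 5 of Section 5.3.1 state "Cycle length = 28 Days".
- Table 3, footnote u: "Post Treatment visits will be performed every 12 weeks". Section 5.4.1: "Post-treatment assessment will be performed every 12 weeks (± 1 week) until" the subject leaves the study. The heading of the post-treatment column in Table 3 also carries the ± 1 week.
- Section 5.3.1.1 assigns these visits, with hematology and a disease assessment, as follows: "For subjects who discontinue study treatment for reasons other than disease progression". Responders who stop treatment while in remission are therefore included.
- On treatment, Table 3 schedules hematology on Day 1 of each cycle from Cycle 2, ± 3 days.

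**The concern.** The number does not match its own gloss, and it may not match its stated purpose. A rule for events after a missed visit should leave alone a subject who missed none. If two on-time post-treatment visits can be more than 91 days apart, a relapse found at the second can be reclassified as censored at the first.

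The subjects exposed are responders who stopped treatment without progression and are then seen about every 12 weeks. Replacing an event with an earlier censoring time removes a downward step from the Kaplan-Meier curve. The smaller risk set makes any steps in between slightly larger, but the net tendency is a longer estimated duration. That is an awkward direction for an analysis meant to test robustness.

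**Working it through.** **Reproducing 91.** Three cycles are 3 × 28 = 84 days, and 12 weeks are 12 × 7 = 84 days. Neither gives 91. Adding one 7-day window does: 84 + 7 = 91. The SAP does not say that this is how the figure was reached.

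**Longest gap between two on-time post-treatment visits.** The protocol does not say what the ± 1 week is measured from, so there are two cases:

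- Window on planned dates: the earlier visit 7 days early and the later one 7 days late give 84 + 7 + 7 = 98 days.
- Window rolling from the previous visit: 84 + 7 = 91 days. No on-time visit exceeds the threshold.

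**On treatment.** Blood counts qualify as assessments, so with cycles starting on time the longest gap is 28 + 3 + 3 = 34 days. On-time treatment visits cannot trigger the rule. Between successive post-treatment visits, Table 3 schedules no other marrow or blood count.

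**How often an on-time gap exceeds 91 days, with windows on planned dates.** The gap is 84 + b − a, where a and b are the two visits' offsets in days. It exceeds 91 when b − a is 8 or more. The distribution of visit dates is not in the documents, so two assumptions bracket it, each with independent offsets, uniform in whole days:

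- Offsets over −7 to +7: 15 × 15 = 225 pairs. A difference of d arises in 15 − d pairs, so d = 8 to 14 gives 7 + 6 + 5 + 4 + 3 + 2 + 1 = 28 pairs. 28/225 = 12.4%. No pair exceeds 98 days.
- Offsets over −3 to +3: 7 × 7 = 49 pairs. The longest gap is 84 + 3 + 3 = 90 days, so 0 of 49.

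**Conditions for a wrongly censored relapse.** The subject must be a responder off treatment, with no new therapy (which already censors under Table 4) and no blood count between visits. The relapse must be dated to the on-time visit itself, and that visit's own count must not be taken as the last assessment.

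**Scale.** SAP Table 7 targets a CR rate of 21% in the 82 subjects at 600 mg, and 0.21 × 82 is about 17 complete responders. The documents do not say how many will be followed off treatment in remission, so no effect on a median can be calculated.

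**The case against.** The strongest reply is that 91 days has a coherent reading. If the ± 1 week applies to the interval, 91 is exactly the longest on-time gap and the rule does what Table 5 says. The wording for the companion survival contacts, in Protocol 5.3.1.1 and 5.4.1, attaches the ± 1 week to the 12-week interval. This stands as a possibility. The placement of the window in the Table 3 column heading points the other way, and neither settles it.

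The progression-assessment paragraph of Protocol 5.3.1.1 also caps the interval at 3 cycles, and Table 3 marks that assessment in the post-treatment column. Taken literally, a 98-day gap breaches the cap. So would any interval above 84 days, which would contradict the protocol's own ± 1 week. A limit counted in cycles fits treated subjects better.

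The mechanism is also narrower than it first looks. Post-treatment visits include a blood count but no scheduled marrow. The progression definition in Protocol 5.3.3 refers to marrow blasts of at least 5%, and 5.3.1.1 repeats the marrow on clinical evidence of recurrence. If a visit's count prompts a later marrow and progression takes the marrow date, the last assessment is that recent count and the rule does not fire. This stands: only relapses dated to the visit, such as clinical progression or a same-day marrow, are exposed.

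Finally, little rests on this analysis. SAP Section 9.0 plans no formal testing. Other variants in 8.1.11 move the opposite way by counting post-treatment therapy or loss to follow-up as events. That lowers the importance but does not make the threshold right.

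**Conclusion.** The three-cycles gloss is wrong under any reading: 84 days, not 91. The threshold allows the visit window on one side only. If windows sit on planned dates, it labels on-time gaps of 92 to 98 days as missed visits. About 0% (visits within ± 3 days) to 12% (visits uniform over ± 7 days) of on-time post-treatment visit pairs could be affected. The effect is confined to this sensitivity analysis of duration of CR, CRh and CR + CRh, where it tends to lengthen the estimate. The main analysis under SAP Table 4 still counts these relapses as events.

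A reader might go further in three ways that the documents do not support:

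- That the schedule definitely permits 98 days. The anchor is not stated.
- That about 1 in 8 relapses found on schedule will be censored. That takes the upper end of the range for visit pairs and applies it to every such relapse, ignoring the conditions above.
- That the sensitivity result is shown to be biased. The direction is a tendency and its size is unknown.

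The on-schedule argument also does not extend to deaths due to progression, which are not tied to visits. This is a small correction that makes the rule match its label.

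**What to change.** In item 3 and Table 5, define a missed assessment as no marrow or hematology collection within the planned visit window, and state what the window is measured from. For post-treatment follow-up in M14-387, with windows on planned dates, this means a gap of more than 98 days. Delete the three-cycles gloss.

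The SAP also covers Study M14-358, whose visit schedule is not in these documents. Its threshold should be checked separately; 98 days should not be carried over.

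The cost is a wording change in two places and the matching programming. The downside is that a slightly longer gap, up to 7 more days (98 − 91), is tolerated before censoring. A genuinely missed visit followed by an on-time one would still be caught, because the shortest such gap is 2 × 84 − 7 − 7 = 154 days. A relapse found between visits on days 92 to 98 after a truly missed visit would pass a plain 98-day cut-off, which is a reason to prefer the window-based definition.

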8.1.12 Exploratory Analysis of MRD Data

The MRD data is collected at baseline, the end of Cycle 1, and every 3 cycles thereafter when bone marrow is collected in Study M14-358 and Study M14-387. The MRD data collected after the first dose of study drug to the last dose of study drug + 7 days, disease progression, clinical progression, the start of new post-treatment therapy, death, or cutoff date, whichever occurs earlier, will be included in the post-baseline MRD analyses.

The MRD analyses include MRD records meeting the following criteria:

1. CD45 value \geq 100,000 and MRD value $<$ 0.1%; or
2. MRD value \geq 0.1%.

Zero is imputed if MRD value is 'less than LLoQ.' Missing MRD is assigned if MRD value is 'too few CD45+ cell.'

The best post-baseline MRD (the lowest) value will be defined as the smallest MRD collected after the first dose of study drug to the last dose of study drug + 7 days, disease progression, clinical progression, the start of new post-treatment therapy, death, or cutoff date, whichever occurs earlier. The median and range will be presented for subjects who

achieved CR, CR + CRh or CR + CRi. The best MRD value will also be categorized to three groups $< 0.1\%$, $\geq 0.1\%$, and Unknown/Missing MRD value. The summary of the best MRD value will be performed among subjects who achieved CR, CR + CRh, or CR + CRi.

OS will also be summarized by the best MRD value ($< 0.1\%$, $\geq 0.1\%$, Unknown/Missing if any) for subjects achieved CR + CRh or CR + CRi. Median survival time with the corresponding 95% CI will be provided from Kaplan-Meier estimation.

OS will also be summarized by the best MRD value ($< 1\%$, $\geq 1\%$, Unknown/Missing if any) for subjects achieved CR + CRh or CR + CRi. Median survival time with the corresponding 95% CI will be provided from Kaplan-Meier estimation.

Duration of CR + CRh will also be summarized by the best MRD value ($< 0.1\%$, $\geq 0.1\%$, Unknown/Missing if any) for subjects achieved CR + CRh. Median duration of CR + CRh with the corresponding 95% CI will be provided from Kaplan-Meier estimation.

Duration of CR + CRi will also be summarized by the best MRD value ($< 0.1\%$, $\geq 0.1\%$, Unknown/Missing if any) for subjects achieved CR + CRi. Median duration of CR + CRi with the corresponding 95% CI will be provided from Kaplan-Meier estimation.

